12.5.1.	Germany-Specific Requirements.....	102

LIST OF TABLES

Table 2-1: Objectives and Endpoints	37
Table 5-1: Details for Study Drug.....	50
Table 6-1: Safety Monitoring After Study Drug Administration.....	61
Table 6-2 DAIDS Table for Grading the Severity of Adult and Pediatric Adverse Events – Systemic.....	66

Table 7-1: Defined Analysis Sets and Descriptions.....	75
Table 7-2: Analyses of Other Secondary Efficacy Endpoints.....	78
Table 7-2: Safety Monitoring and Interim Analyses.....	81
Table 10-1: Pausing Guidelines	86
Table 12-1: Schedule of Assessments.....	96

LIST OF FIGURES

Figure 3-1: Study Design Schematic for ADG20-TRMT-001	42
---	----

PROTOCOL SYNOPSIS

Sponsor:	Adagio Therapeutics, Inc.
Protocol No.	ADG20-TRMT-001
Title of Study:	A Phase 2/3 Randomized, Double-Blind, Placebo-Controlled Trial to Evaluate the Efficacy and Safety of ADG20 in the Treatment of Ambulatory Participants with Mild or Moderate COVID-19 (STAMP)
Study Drug:	ADG20
Study Phase:	2/3
Indication	COVID-19
US IND No.	152327
EudraCT No.	2020-006082-11
No. of Sites/Location:	Approximately 100 to 115 sites / global

Objectives and Endpoints

Objectives	Endpoints
Primary	
To evaluate the efficacy of ADG20 compared to placebo in the treatment of mild or moderate COVID-19 in participants at high risk of disease progression	COVID-19-related hospitalization or all-cause death through Day 29
To evaluate the safety and tolerability of ADG20 compared to placebo through Day 29 in participants with mild or moderate COVID-19 and high risk of disease progression	Assessment of safety through Day 29 based on: 
• The incidence of TEAEs• Incidence of solicited injection site reactions through Day 4• Changes from baseline in clinical laboratory tests (ie, CBC with differential, serum chemistry, coagulation)• Changes from baseline in vital signs (body temperature, heart rate, respiration rate, and systolic and diastolic blood pressure)
Secondary	

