Resistance to ADG20 in viral isolates obtained from participants will be characterized using genotypic methods, with phenotypic methods deployed as appropriate. The impact of host biomarkers, such as baseline SARS-CoV-2 antibody responses, and viral load, on selected outcomes, may be evaluated.

Pharmacokinetic and Immunogenicity Assessments

Blood samples will be collected at specified time points for assessments of PK and to evaluate immunogenicity (anti-drug antibodies) to ADG20.

Safety Assessments

Safety will be assessed in an ongoing manner. Participants will receive ADG20 or placebo. As a precaution for acute worsening of disease, hypersensitivity, and injection site reactions (ISRs), participants will be observed after study drug administration as described in Section 6.4.1 of the protocol. If any hypersensitivity reactions occur, the iDMC will review available safety data and

provide a recommendation regarding the duration of monitoring. Participants will then be followed via telemedicine visits, phone calls, or in-person visits as described in the Schedule of Assessments through Day 29 for safety assessments.

Safety assessments will include monitoring of AEs, clinical laboratory testing, vital sign measurements (body temperature, heart rate, respiration rate, and systolic and diastolic blood pressure), and physical examinations. Any AESIs (hypersensitivity reactions through Day 4) will be recorded. Hypersensitivity reactions occurring after Day 4 will be recorded as AEs.

Participants will record any ISRs using the Injection Site Reaction Diary starting after dosing on Day 1 through Day 4 (Appendix 12.3). Other AEs, including SAEs and medically attended adverse events (MAAEs) (including new onset chronic illnesses), will be collected through the Month 14/EOS visit.

For the purposes of this study, worsening or sequelae of the index case of COVID-19 will not be recorded as AEs, unless they meet SAE criteria. These data will be captured as efficacy assessment data as these are expected endpoints. Subsequent episodes of COVID-19 in the same participant will be captured according to standard AE processes, including the standard process for expedited reporting of SAEs if the event meets the definition of an SAE.

Details of Applicable Monitoring Committee

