The incidence of TEAEs (including solicited ISRs), SAEs, TEAEs related to study drug, SAEs related to study drug, TEAEs leading to study drug discontinuation, AESIs, and MAAEs will be summarized by MedDRA system organ class (SOC), preferred term (PT), and treatment group.

The incidence of study drug related TEAEs (including solicited ISRs) will also be summarized by maximum severity by SOC, PT, and treatment group.

The incidence of solicited AEs (ISRs) will be summarized by maximum severity through Day 4. The maximum duration and time from injection to report of first onset of any solicited ISR will also be summarized.

Descriptive statistics for clinical laboratory results and vital sign parameters and for the change from baseline will be presented by treatment group and time point assessed. Potentially clinically significant laboratory and vital sign parameters will be summarized by treatment group and time point assessed.

Immunogenicity Analyses

Immunogenicity data will be listed and summarized in tables using descriptive statistics.

LIST OF ABBREVIATIONS

Abbreviation	Definition
ACIP	Advisory Committee on Immunization
ADA	anti-drug antibodies
ADE	antibody-dependent enhancement (of disease)
AE	adverse event
AESI	adverse event of special interest
ANCOVA	analysis of covariance
BLQ	below the limit of quantification
BMI	body mass index
CBC	complete blood count
CDC	Centers for Disease Control and Prevention
CFR	Code of Federal Regulations
CI	confidence interval
CONSORT	Consolidated Standards of Reporting Trials
COPD	chronic obstructive pulmonary disease
COVID-19	coronavirus disease 2019
CRO	contract research organization
CV%	coefficient of variation
DAIDS	Division of AIDS (National Institute of Allergy and Infectious Disease)
eCRF	electronic case report form
eGFR	estimated glomerular filtration rate
eCRF	electronic case report form
ELF	epithelial lining fluid
EMA	European Medicines Agency
EOS	end of study
EU	European Union
EUA	emergency use authorization
FAS	full analysis set
Fc	fraction crystallizable
FDA	Food and Drug Administration
FiO ₂	fractional inspired oxygen
FSH	follicle stimulating hormone
GCP	Good Clinical Practice
GLP	Good Laboratory Practice
IA	interim analysis

Abbreviation	Definition
IB	Investigator's Brochure
IC ₅₀	Half-maximal inhibitory concentration
ICF	informed consent form
ICH	International Council for Harmonisation
ICU	intensive care unit
iDMC	independent data monitoring committee
IEC	independent ethics committee

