2. STUDY OBJECTIVES, ENDPOINTS, AND DEFINITIONS

2.1. Objectives and Endpoints

The objectives and endpoints are presented in [Table 2-1](#).

Table 2-1: Objectives and Endpoints

Objectives	Endpoints
Primary	
To evaluate the efficacy of ADG20 compared to placebo in the treatment of mild or moderate COVID-19 in participants at high risk of disease progression	COVID-19-related hospitalization or all-cause death through Day 29
To evaluate the safety and tolerability of ADG20 compared to placebo through Day 29 in participants with mild or moderate COVID-19 and high risk of disease progression	Assessment of safety through Day 29 based on: 
• The incidence of TEAEs• Incidence of solicited injection site reactions through Day 4• Changes from baseline in clinical laboratory tests (ie, CBC with differential, serum chemistry, coagulation)• Changes from baseline in vital signs (body temperature, heart rate, respiration rate, and systolic and diastolic blood pressure)
Secondary	
To evaluate the effect of ADG20 on the following clinical parameters in participants with mild or moderate COVID-19 and high risk of disease progression 
• Severity of COVID-19• COVID-19-related emergency room visits, COVID-19-related hospitalizations, or all-cause death• Time to sustained resolution of COVID-19 symptoms• COVID-19-related medically attended visits• Time to sustained recovery of COVID-19 symptoms• All-cause mortality	
• Severe/critical COVID-19 or all-cause death through Day 29• COVID-19-related emergency room visits, COVID-19-related hospitalization, or all-cause death through Day 29• Time to sustained resolution of COVID-19 symptoms through Day 29• COVID-19-related medically attended visit (telemedicine, physician office, urgent care center, emergency room, hospitalization) or all-cause death through Day 29• Time to sustained recovery defined as sustained improvement or resolution of COVID-19 symptoms through Day 29• All-cause death through Day 29, Day 60, and Day 90

Objectives	Endpoints

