6.4.6.1.2. Serious Adverse Events

An SAE is defined as any event that:

- results in death
- is immediately life-threatening
- requires inpatient hospitalization or prolongation of existing hospitalization
- results in persistent or significant disability/incapacity
- is a congenital anomaly/birth defect

Immediately life-threatening: report if suspected that the patient was at substantial risk of dying at the time of the adverse event, or use or continued use of the medical product might have resulted in the death of the patient.

Inpatient hospitalization: report as an SAE if admission to the hospital or prolongation of hospitalization was a result of an adverse event.

Emergency room visits that do not result in admission to the hospital should be evaluated for one of the other serious outcomes (eg, life-threatening; required intervention to prevent permanent impairment or damage; other serious medically important event).

Important medical events that may not result in death, be life-threatening, or require hospitalization may be considered SAEs when, based upon appropriate medical judgment, they may jeopardize the participant or may require medical or surgical intervention to prevent one of the outcomes listed in this definition. Examples of such medical events include allergic bronchospasm requiring intensive treatment in an emergency room or at home, blood dyscrasias or convulsions that do not result in inpatient hospitalization, or the development of drug dependency or drug abuse.

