6.4.6.3.2. Exceptions

For the purposes of this study, worsening or sequelae of the index case of COVID-19 will not be recorded as AEs, unless they meet SAE criteria. These data will be captured as efficacy assessment data as these are expected endpoints. Subsequent episodes of COVID-19 in the same participant will be captured according to standard AE processes, including the standard process for expedited reporting of SAEs if the event meets the definition of an SAE.

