5.8.1.9. Analysis of Adverse Events and Injection Site Reactions

All AE and ISR analyses will be performed using the Safety Set. For all analyses of AEs/ISR, if the same AE/ISR (based on PT) is reported for the same participant more than once, the AE/ISR is counted only once for the PT and at the highest severity and by relationship to study drug.

Percentages will be calculated based on the number of participants in each treatment group in the Safety Set. Missing and incomplete dates of AEs will be imputed as described in [Appendix D](#). In addition to safety summaries, listings of AEs (with TEAE designated by *), SAEs, and ISRs will be presented.

Safety summaries will be presented through Day 29 and overall. All summaries will be sorted by decreasing frequency of SOC/PT in the ADG20 arm. The AE/ISR summaries listed below will be provided:

- Overall summary of AEs (solicited and unsolicited) including the number/percentage of participants with:
 - a pre-treatment AE
 - a TEAE (and separately for unsolicited and solicited TEAEs)
 - a study drug related TEAE
 - \geq Grade 3 TEAE
 - an SAE
 - a study drug related SAE
 - a TEAE leading to death

- a study drug related TEAE leading to death
- a TEAE leading to treatment discontinuation
- an MAAE
- any hypersensitivity reaction (and separately for any hypersensitivity reaction through Day 4 [AESI])
- Incidence of TEAEs (including solicited ISRs) by SOC, PT, and treatment group
- Incidence of TEAEs (including solicited ISRs) occurring in >2% of participants in either arm by PT sorted by descending frequency of PT in the ADG20 arm
- Incidence of MAAE by SOC, PT, and treatment group
- Incidence of study drug related TEAEs (including solicited ISRs) by SOC, PT, and treatment group.
- Incidence of TEAEs (including solicited ISRs) by maximum severity by SOC, PT and treatment group
- Incidence of study drug related TEAEs (including solicited ISRs) by maximum severity by SOC, PT, and treatment group
- Incidence of solicited AEs (ISRs) and by maximum severity based on the FDA toxicity scale through Day 4 (only for Day 29 analysis)
- Incidence of SAEs by SOC, PT, and treatment group
- Incidence of SAEs excluding COVID-19 SAEs associated with the primary endpoint by SOC, PT, and treatment group; COVID-19-related PTs include COVID-19, COVID-19 pneumonia.
- Incidence of study drug related SAEs by SOC, PT, and treatment group

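### Serious index COVID-19 events count as TEAEs and are removed from one SAE table only, so if ADG20 works, the participant-level TEAE totals carry the efficacy difference and can mask other harm

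*Protocol*

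**What the plan says.** - **Recording rule.** The Protocol Synopsis (Safety Assessments) and Protocol 6.4.6.1.1 and 6.4.6.3.2 say that "worsening or sequelae of the index case of COVID-19 will not be recorded as AEs, unless they meet SAE criteria". Section 6.4.6.3.2 adds: "These data will be captured as efficacy assessment data as these are expected endpoints". Later COVID-19 episodes follow the ordinary AE process.
- **Seriousness.** Protocol 6.4.6.1.2 lists death and an event that "requires inpatient hospitalization or prolongation of existing hospitalization".
- **Primary efficacy endpoint.** Protocol 2.1: "COVID-19-related hospitalization or all-cause death through Day 29".
- **Primary safety endpoint.** The first item listed in Protocol 2.1, through Day 29, is "The incidence of TEAEs". The others are injection site reactions, laboratory tests and vital signs.
- **TEAE definition.** Protocol 7.11 and SAP 5.8.1.3 count any AE starting during or after dosing, with no exception for COVID-19.
- **Outputs.** Protocol 7.11 plans summaries of "The incidence of TEAEs (including solicited ISRs), SAEs, TEAEs related to study drug, SAEs related to study drug" and further categories. SAP 5.8.1.9 includes "Incidence of TEAEs (including solicited ISRs) by SOC, PT, and treatment group", the same by maximum severity, and overall rows for any TEAE, Grade 3 or higher TEAE and fatal TEAE. Only one output there removes index events: "Incidence of SAEs excluding COVID-19 SAEs associated with the primary endpoint by SOC, PT, and treatment group". It names two preferred terms, COVID-19 and COVID-19 pneumonia.
- **Periods.** Summaries run through Day 29 and overall.

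**The concern.** The same clinical events feed the primary efficacy endpoint and the first component of the primary safety endpoint. If ADG20 prevents admissions, it lowers TEAE incidence for a reason unrelated to tolerability. An excess of other events can then be offset in the participant-level rows. The SAP recognises the overlap for SAEs but does not carry the solution to TEAEs, so non-serious Grade 3 events have no total free of index COVID-19.

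Preferred-term rows cannot replace that total. One participant may appear under several terms, so counts cannot be summed across terms, and an excess spread thinly over many terms shows only in a participant-level row.

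The overall tables to Month 14 add a second problem. Later COVID-19 episodes are AEs and would naturally code to the same terms as the index illness. Protocol 1.4.2 links disease enhancement to suboptimal antibody titres, so later episodes need to be visible separately.

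**Working it through.** **Inputs.** SAP 4.2 gives a placebo rate of 12%, a relative risk reduction of 70%, about 320 non-Omicron participants and 399 randomised. SAP 4.5.6 puts all dosed participants in the Safety Set. The documents give no background rate for other TEAEs, so those below are assumptions.

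**1. The plan's own figure.** The ADG20 rate is 0.30 × 12% = 3.6%. With 160 per arm, two-sided 0.05 and pooled variance, z = (0.084 × √160 − 1.96 × √(2 × 0.078 × 0.922)) / √(0.12 × 0.88 + 0.036 × 0.964) = 0.85. Power is 80.3%, against the stated 80% or so. The rates are those the sponsor planned on.

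**2. Gap from index events.** 12% − 3.6% = 8.4 points in non-Omicron participants, or about 19 versus 6 participants (160 × 0.12 = 19.2; 160 × 0.036 = 5.8). If all 399 are dosed and the other 79 add no difference, the Safety Set gap is 8.4 × 320/399 = 6.7 points. The SAP also reports a blinded pooled rate of about 9%, whereas 12% and 3.6% average 7.8%. A pooled 9% with the same efficacy implies 0.09/0.65 = 13.8% on placebo, and gaps of 9.7 and 7.8 points.

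**3. Any-TEAE row with no true harm.** Assuming independence, row rate = 1 − (1 − index)(1 − other), so the gap is index gap × (1 − other). At an assumed 20% background it is 8.4 × 0.80 = 6.7 points; at 30%, 5.9. Over the Safety Set these are 5.4 and 4.7.

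**4. Grade 3 or higher row with a true doubling of other events.** Example, all index events Grade 3 or higher, 3% doubled to 6%: placebo 1 − 0.88 × 0.97 = 14.6%; ADG20 1 − 0.964 × 0.94 = 9.4%; relative risk 0.64. The half-share rows use index rates of 6% and 1.8%. The Safety Set rows multiply index rates by 320/399 = 0.802, which treats Omicron participants as having no serious index events.

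| Index events Grade 3 or higher | Population | Other events 3% to 6% | Other events 4% to 8% |
|---|---|---|---|
| All | Non-Omicron | 14.6% v 9.4%, RR 0.64 | 15.5% v 11.3%, RR 0.73 |
| All | Safety Set | 12.3% v 8.7%, RR 0.71 | 13.2% v 10.7%, RR 0.80 |
| Half | Non-Omicron | 8.8% v 7.7%, RR 0.87 | 9.8% v 9.7%, RR 0.99 |
| Half | Safety Set | 7.7% v 7.4%, RR 0.96 | 8.6% v 9.3%, RR 1.08 |

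If Omicron participants instead have the 12% rate in both arms, the ADG20 index rate over the Safety Set is 0.802 × 3.6% + 0.198 × 12% = 5.3%. The all-Grade-3 results become 14.6% v 10.9% (RR 0.75) and 15.5% v 12.8% (RR 0.83). With index events removed, the relative risk is 2.0 in every case.

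**The case against.** A reader might infer that the plan has a fixed bias towards ADG20, or that the primary safety objective cannot be read from its own tables. The documents support neither.

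- **The gap is conditional.** Without efficacy it is zero, and if ADG20 worsened the index illness it would reverse. Safety is summarised descriptively, with no planned hypothesis test.
- **Much other harm stays visible.** Day 29 tables show each preferred term, also by severity. SAP 5.8.2 splits deaths by primary cause and by COVID-19 contribution, which largely answers the fatal row. Medically attended AEs leave out COVID-19 by definition (SAP 5.8.1.5). Study drug-related events have their own tables, and serious events have the excluding table.
- **The overlap is near-complete, not exact.** The efficacy endpoint includes deaths from other causes and emergency-room stays of 24 hours or more; Protocol 6.4.6.1.2 requires an emergency visit without admission to meet another seriousness criterion.
- **Seriousness is not grade.** A serious index event need not be Grade 3 or higher, hence the half-share rows.
- **Removal would not make harm conclusive.** At about 200 per arm, 3% versus 6% is 6 versus 12 participants (Fisher p = 0.23; about 30% power).

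It is also tempting to make the COVID-excluded tables the primary safety comparison. That would demote the signal for the theoretical risk named in Protocol 1.4.2, a paradoxical increase in disease severity, which would appear as serious worsening of the index case.

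All these points stand. None supplies a participant-level any-TEAE or Grade 3 or higher total without index COVID-19.

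**Conclusion.** The concern holds in a limited form. Nearly all primary efficacy events also count as TEAEs, and only one SAE table removes them. If ADG20 works as planned, the any-TEAE and Grade 3 or higher rows and the SOC totals carry part of that benefit and can mask an excess of other events; they do not necessarily do so. The step from 8.4 or 6.7 points of index events to the displayed relative risks depends on assumed background rates, on independence, on the share of index events graded 3 or higher, and on the Omicron participants' event rate. Across the cases tabulated, a true doubling displays between 0.64 and 1.08. This is a cheap improvement to the safety displays, not a defect that invalidates them.

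**What to change.** In SAP 5.8.1.9:

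1. Keep the all-inclusive tables as the main display.
2. Add supplementary any-TEAE and Grade 3 or higher TEAE rows, and TEAE tables by SOC/PT and by maximum severity, that exclude serious events of the index COVID-19 case.
3. Define the exclusion by a flag for index versus later episode, assigned while blinded, and not only by the two named preferred terms. Index events coded elsewhere, such as to respiratory failure, are then caught, and later episodes are not dropped, as could happen if the exclusion were programmed by term alone.
4. In the overall (Month 14) tables, show later COVID-19 episodes on their own line by maximum severity.

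The cost is a few extra programmed tables and a blinded episode assignment for each COVID-19 AE. That assignment goes somewhat beyond what the existing SAE table needs. SAP 3.2 has the SAP signed before unblinding, so the rule can be fixed in time.

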1. INTRODUCTION

1.1. ADG20 Background

ADG20 (also known as adintrevimab) is a fully human monoclonal immunoglobulin G1 antibody targeted to the spike glycoprotein of SARS-CoV-2. ADG20 binds with high affinity to a conserved epitope in the RBD of the spike protein of SARS-CoV-2 and related Clade 1 sarbecoviruses and displays broad and potent in vitro neutralizing activity against SARS-CoV-2, SARS-CoV, SARS-CoV-2 D614G, and the bat SARS-like viruses WIV1-CoV and SHC014-CoV. In addition to potent neutralization, ADG20 displays Fc-mediated innate immune effector activity, including antibody-dependent cellular cytotoxicity, antibody-dependent cellular phagocytosis, and antibody-dependent complement deposition. The Fc region of ADG20 has also been engineered to contain the Fc heavy chain modification LA (M435L, N441A), resulting in an estimated half-life of approximately 97 days in humans based on preliminary data from a Phase 1 study (ADG20-1-001) in healthy adult volunteers. No ADG20-specific off target binding to human tissues was observed in adult and fetal human tissue cross-reactivity and immunohistochemistry studies, and ADG20 was not associated with any toxicologically relevant or clinically meaningful findings during or at the end of the in-life portion in a repeat-dose rat toxicology study.

1.1.1. Nonclinical Studies of ADG20

Given the rising prevalence of SARS-CoV-2 variants, nonclinical studies evaluating the ability of ADG20 to bind to and neutralize known and emerging variants of concern are performed on an ongoing basis. ADG20 has displayed potent binding and neutralizing activity against multiple SARS-CoV-2 variants of concern, including B.1.1.7 (Alpha), B.1.351 (Beta), P.1 (Gamma), and B.1.617.2 (Delta) ([Dejnirattisai 2021](#)). In vitro activity has been demonstrated against variants that have shown relative or absolute resistance to a subset of other clinical stage SARS-CoV-2 mAb products ([Dejnirattisai 2021](#); [Liu 2021a](#); [Liu 2021b](#); [Planas 2021](#); [Starr 2021](#); [Wang 2021](#); [Dejnirattisai 2022](#)) and that have been associated with lower rates of vaccine efficacy ([Madhi 2021](#); [Mahase 2021](#); [Voysey 2021](#)). In addition, ADG20 displayed in vitro binding and/or neutralizing activity against the SARS-CoV-2 variant B.1.1.529 BA.1 (Omicron), albeit with reduced potency compared to activity against prior variants ([Liu 2021b](#); [Planas 2021](#); [Starr 2021](#); [Wang 2021](#)). The nonclinical program includes in vitro studies evaluating the avid and monovalent binding by ADG20 to SARS-CoV-2 RBDs incorporating mutations present in known and emerging variants and in vitro neutralization assays using authentic virus variants and pseudovirus. A detailed review of nonclinical experience with ADG20 is provided in the IB.

